6.3 Screening

The following steps and information will be performed/completed up to 7 days prior to the treatment day:

- Informed Consent
- Demographics/Medical/Ocular history
- Concomitant Systemic and Ophthalmic Meds

6.4 Pre-Treatment/Baseline Assessment

The following assessments will be performed on Day 0, **prior to** treatment (**Note: the OSDI, Discomfort, and Pain Questionnaires must be administered prior to clinical evaluations**):

Table 1: Subject Assessments

Assessment	Description
Discomfort and Pain Questionnaires	The Pain Questionnaire (provided in Appendix C) is a Linkert scale questionnaires using a scale of 0-10 with anchored descriptions for the scale. The Discomfort Questionnaire is a visual analog scale (VAS) questionnaire using a scale from 0-100% to assess eye discomfort. Both questionnaires are to be self-assessed by the subject prior to any clinical assessment.
OSDI	Scoring that evaluates patient symptoms based on a validated questionnaire [7] using a Linkert scale. (see questionnaire provided in Appendix B). OSDI questionnaires include 12 questions in 3 categories asked of the subjects by clinicians who circle a number next to a description that best represents the subject's answer on a paper form. The numbers for each category are totaled and the total OSDI score is calculated by the formula: sum of scores x 25/# of questions answered. Dry eye severity is then assessed using the chart on the 2 nd page of the questionnaire.
Uncorrected Visual Acuity	Single letter scoring with an ETDRS high contrast test face at the test distance corresponding to the ETDRS chart used
Keratometry	Test of corneal curvature conducted using a manual keratometer or using simulated keratometry from corneal topography
Manifest Refraction	Manual test of refraction to determine optimum prescriptive lenses required by the subject to obtain 20/20 vision
BSCVA	Single letter scoring with an ETDRS high contrast test face at the test distance corresponding to the ETDRS chart used
Slit Lamp for Anterior Segment Health	Using biomicroscopy to examine anterior segment including lids, adnexa, conjunctiva, sclera, corneal clarity, and surface integrity, anterior chamber, and iris Grading system: 
 • 0=No clinical findings • 1=Non-clinically significant positive findings (including pterygium, pinguecula, corneal scar, conjunctival pigment, corneal arcus, verucca, non-visual significant lens changes) • 2=Abnormal findings
Lid Margin Abnormalities	Scored 0-4 based on the number of the following present in each eye: 
 • irregular lid margin • vascular engorgement • plugged meibomian gland orifices • anterior or posterior replacement of the mucocutaneous junction
Eyelid Margin Assessment	Development of any of the following: 
 • entropion or ectropion • floppy eyelids • loss of lash integrity

Assessment	Description
Tear Break-Up time	
 • Use AMCON 0.12mg Fluorescein strips • Apply one or two drops of non-preserved saline to the impregnated paper tip. Excess fluid will automatically fall off. Shaking is neither required nor desirable. • Ask the patient to look down and in. • Gently touch the strip to the superior temporal bulbar conjunctiva for one or two seconds • Ask the patient to blink three times and open eyes naturally • Immediately measure the time between the last blink and the first appearance of a dark spot on the cornea (formation of dry area) • Time shall be recorded in seconds and shall be the average of three consecutive measurements • Repeat with a new strip for the second eye
Corneal Fluorescein Staining Slit Lamp Evaluation	
National Eye Institute (NEI) corneal grading scale evaluating five corneal regions:
 
 • superior • inferior • central • temporal • central 
Each graded on a 0-3 scale (0=normal-no staining; 1=mild-superficial stippling micropunctate staining; 2=moderate-macropunctate staining with some coalescent areas; 3=severe-numerous coalescent macropunctate areas and/or patches) [8]

Meibomian Gland Assessment and Scoring	
Note: Meibomian Gland Assessments must be made by a rater not involved in the study procedure and blinded to the arm to which the subject is randomized
 
 • Assess lower eyelids using Meibomian Gland Evaluator while viewing the eyelid margin using slit lamp microscope • Evaluate 15 glands in 3 zones (nasal, medial, temporal) • Each gland graded from 0 to 3 • Maximum MGS score=45 in each eye [5, 6]
Intraocular Pressure	Measured by a Goldmann tonometer and recorded in mmHg

6.5 Randomization

Prior to randomization it must be determined that the subject meets all entrance criteria. This includes the completion of all screening tests to determine eligibility. The randomization schedules with subjects allocated to the iLux or control LipiFlow group in a 1:1 ratio will be prepared for each site. Each envelope will have a sequential envelope number on the outside, and contain the assigned treatment procedure inside. Before the treatment, the assigned personnel will open the lowest numbered envelope. The envelope number will be documented on the study source documents and in the EDC. Randomization will take place at the treatment visit prior to subject treatment. There are no criteria for crossover in this study, so all subjects must be treated according to the arm to which they are randomized.

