
Clinical Sites
	
 • Dishler Laser Institute, Greenwood Village, CO • Tauber Eye Center, Kansas City, MO • Gordon Schanzlin New Vision Eye Institute, La Jolla, CA • Eyecare Consultants – Vision Source, Engelwood, CO • Barnet-Dulany-Perkins Eye Center, Phoenix, AZ • Schwartz Laser Eye Center, Scottsdale, AZ • Pepose Vision Institute, Chesterfield, MO • Other sites TBD

Procedure
	
Treatment of eyes per Instructions for Use (IFU) for the device to which the subject was randomized

Statistical Analysis
	
Categorical or binary endpoints will be summarized by count and percentage. Analysis of covariance (ANCOVA) will be used to assess the treatment effect between baseline and 4 weeks for iLux and LipiFlow treatments for the primary and secondary effectiveness endpoints. For each endpoint analyzed, the baseline value will be used as a covariate. Given that non-inferiority is demonstrated for the iLux endpoints, success will not be claimed unless the mean change from baseline in the test arm is clinically significant and significantly different from zero.

Schedule of Evaluations
	
Screening (Day -7 to Day 0)
 
 • Informed Consent • Demographics/medical/ocular history • Concomitant systemic and ophthalmic meds <hr/> 
Pre-Treatment/Baseline (Day 0)
 
 • Pain and Discomfort Questionnaires (self-assessed after treatment but prior to any clinical assessment) • OSDI • Uncorrected visual acuity • Keratometry • Manifest refraction • BSCVA • Slit Lamp for Anterior Segment Health

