7 DATA ANALYSIS

Descriptive statistics will be provided to summarize outcomes at each visit as well as for change from baseline. Continuous endpoints will be summarized with N, mean, standard deviation, minimum, maximum, and median. Categorical or binary endpoints will be summarized by count and percentage. Analysis of covariance (ANCOVA) will be used to assess the treatment effect between baseline and 4 weeks for iLux and LipiFlow (LF) treatments for the primary and secondary effectiveness endpoints. For each endpoint analyzed, the baseline value will be used as a covariate.

Given that non-inferiority is demonstrated for the iLux endpoints, success will not be claimed unless the mean change from baseline in the test arm is clinically significant and significantly different from

zero. For any endpoints for which non-inferiority is demonstrated and mean changes from baseline are clinically significant and significantly different from zero, a test for superiority will be performed.

All subjects enrolled and treated in the study shall be included as part of the safety analysis.

Subjects who are randomized but not treated for any reason will be included in the intent-to-treat analysis as part of the arm to which they are randomized but they will be excluded from the per-protocol analysis.

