7.2 Non-Inferiority Compared to Control

7.2.1 Primary Effectiveness Endpoints Hypothesis

7.2.1.1 MGS

The co-primary effectiveness endpoint, MGS, will be tested for non-inferiority against LipiFlow using a 5-point non-inferiority delta (δ) in a one-tailed test.

It is hypothesized that the MGS mean score from the iLux group will not be lower than (not inferior to) the MGS mean score from the LipiFlow group at the 4-week exam:

Null Hypothesis: $\mu (\text{iLux-MGS} - \text{LF-MGS}) + \delta \leq 0$

Alternate Hypothesis: $\mu (\text{iLux-MGS} - \text{LF-MGS}) + \delta > 0$

Where $\mu (\text{iLux-MGS} - \text{LF-MGS})$ is the mean difference in the MGS between iLux and LipiFlow from baseline to week 4 and $\delta = 5$.

The MGS was found to be highly correlated across eyes in the previously completed pilot study data (correlation of 0.68); consequently, OD and OS values will be averaged to form an overall person score. An ANCOVA model, with baseline MGS as a covariate, will be used to assess the difference between the LipiFlow System and the iLux System results. The lower boundary of the least square means group confidence interval will be tested against the non-inferiority boundary of 5 points. To be successful, the lower boundary of the confidence interval must exceed -5.

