7.2.1.2 TBUT

The co-primary endpoint, Tear Break-Up Time (TBUT) will be tested for non-inferiority against LipiFlow using a 2.5-second non-inferiority delta (δ) in a one-tailed test. A similar ANCOVA model will be used to compare TBUT between devices, with covariate adjustment for baseline TBUT. It is hypothesized that the TBUT mean time for the iLux group will not be less than (not inferior to) the TBUT mean time for the LipiFlow group at the 4-week exam:

Null Hypothesis: $\mu (\text{iLux-TBUT} - \text{LF-TBUT}) + \delta \leq 0$

Alternate Hypothesis: $\mu (\text{iLux-TBUT} - \text{LF-TBUT}) + \delta > 0$

Where $\mu (\text{iLux-TBUT} - \text{LF-TBUT})$ = mean difference in the TBUT between iLux and LipiFlow from baseline to week 4 and $\delta = 2.5$.

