7.2.2 Secondary Effectiveness Endpoint Analysis

If the co-primary effectiveness endpoints demonstrate non-inferiority, the secondary effectiveness endpoint, change from baseline in Ocular Surface Disease Index (OSDI) at the 4-week exam, will be compared against the control device to test for non-inferiority. A similar ANCOVA model will be used to compare OSDI between devices, with covariate adjustment for baseline OSDI.

It is hypothesized that the OSDI mean score from the iLux group will not be lower than (not inferior to) the OSDI mean score from the LipiFlow group at the 4-week exam:

Null Hypothesis: $\mu (\text{iLux-OSDI} - \text{LF-OSDI}) - \delta \geq 0$

Alternate Hypothesis: $\mu (\text{iLux-OSDI} - \text{LF-OSDI}) - \delta < 0$

Where $\mu (\text{iLux-OSDI} - \text{LF-OSDI})$ = mean difference in the OSDI between iLux and LipiFlow from baseline to week 4 and $\delta = 7$.

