7.2.6 Poolability Analysis

Subject demographic characteristics and background variables shall be summarized. To ensure poolability, primary effectiveness endpoints will be compared across site and gender. Analysis of variance will be used to test mean effects and interaction of stratification variables of treatment. A p-value of 0.15 will be used for these assessments.

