7.2.7 Missing Data

Primary and secondary effectiveness endpoints will be imputed when missing to preserve the randomization in the intent-to-treat analysis population. The primary method of imputation used will be by multiple imputation. Ten imputations will be produced for each endpoint using SAS PROC MI. The seed used to begin random number generation will be 11142016. The Markov chain Monte Carlo method will be used to compute with the following predictor variables: baseline tear break-up time, baseline MGS score, gender, and age. Alternate imputation methods used to assess sensitivity to the presence of missing data will be last observation carried forward (LOCF), best case (a test subject's best prior value and a predicate subject's worst prior value is imputed) and worst case (a test subject's worst prior value and a predicate subject's best prior value is imputed). If best case and worst case

conclusions differ, a tipping point analysis will be performed. In the absence of post-treatment data, baseline values will be used for imputation for alternate imputation methods.

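### Randomization schedules are prepared per site, but the MGS, TBUT and OSDI ANCOVAs omit site; adding it is an optional, low-cost gain in precision if schedules are blocked and sites differ

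*Combined protocol and SAP*

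**What the plan says.** **Randomization.** Section 6.5: "The randomization schedules with subjects allocated to the iLux or control LipiFlow group in a 1:1 ratio will be prepared for each site". Sites open numbered envelopes in sequence. Blocking and block size are not mentioned. At least 7 sites are planned; the synopsis names seven and adds "Other sites TBD".

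**Main models.** Section 7 sets the general rule: "For each endpoint analyzed, the baseline value will be used as a covariate". Section 7.2.1.1 applies it to MGS: "An ANCOVA model, with baseline MGS as a covariate, will be used to assess the difference". Section 7.2.1.2 does the same for TBUT: "A similar ANCOVA model will be used to compare TBUT between devices, with covariate adjustment for baseline TBUT". Section 7.2.2 follows for OSDI: "A similar ANCOVA model will be used to compare OSDI between devices, with covariate adjustment for baseline OSDI". None of these names site.

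**Where site appears.** Section 7.2.6 compares the co-primary endpoints by site and gender at a threshold of 0.15: "Analysis of variance will be used to test mean effects and interaction of stratification variables of treatment". It states no consequence for the main models and does not cover OSDI.

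**Imputation.** Section 7.2.7 imputes "with the following predictor variables: baseline tear break-up time, baseline MGS score, gender, and age". Site, treatment arm and baseline OSDI are not on that list.

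**The concern.** If each site's schedule keeps the arms balanced, differences between sites largely cancel out of the treatment comparison. A model without site does not know this. Whatever site variance remains after baseline adjustment stays in its error term, so the confidence interval tested against the margin is wider than it need be.

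Site differences are plausible here: MGS is a gland-by-gland grade, TBUT is a timed visual reading, and staff will presumably differ between sites. At stake is some power. For the co-primaries it is already high; OSDI, planned at 80% and tested only after both co-primaries succeed, has more to gain.

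**Working it through.** **Inputs from Section 7.2.4:** 128 subjects, taken as 64 per arm (1:1); margins 5, 2.5 and 7; SDs 8, 4 and 14. Alpha 0.025 is stated for OSDI and, one-sided, also reproduces the co-primary power. **Assumption:** the site share of variance left after baseline adjustment, taken as 0, 5, 10 and 20%, because the documents give no value.

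**1. The plan's own figures.** The standard error is SD × √(2/64). For MGS this is 8 × 0.1768 = 1.414, so margin/SE = 5/1.414 = 3.54. TBUT has the same ratio. For OSDI, SE = 2.475 and the ratio is 7/2.475 = 2.83. The noncentral t with 126 df gives 0.939, 0.939 and 0.801, and 0.939² = 0.882. All stated figures reproduce with no site term.

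**2. What site does under within-site balance.** Take MGS at a 20% share.
- The interval half-width without site stays near 2.80.
- The estimate's actual SE is 1.414 × √0.80 = 1.265.
- With site in the model (7 sites, 6 df spent), the half-width is 2.51.
- Approximate power without site: Φ((5 − 2.80)/1.265) = Φ(1.74) = 0.959.
- Approximate power with site: Φ((5 − 2.505)/1.265) = Φ(1.97) = 0.976, a gain of about 1.7 points.

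**3. Simulation.** 8 sites of 16, blocks of 4, baseline covariate in both models, stated SDs read as residual after baseline and including site, 100,000 trials per cell. Power without → with site:

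| Assumed site share | MGS (TBUT the same) | OSDI |
|---|---|---|
| 0% | 0.937 → 0.937 | 0.798 → 0.797 |
| 5% | 0.942 → 0.947 | 0.803 → 0.815 |
| 10% | 0.947 → 0.957 | 0.812 → 0.836 |
| 20% | 0.958 → 0.975 | 0.829 → 0.876 |

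Across the 7- and 8-site layouts, the change per co-primary is −0.1 to 0, +0.4 to +0.5, +0.9 to +1.0 and +1.5 to +1.7 points. For OSDI it is −0.2 to 0, +1.0 to +1.2, +2.3 to +2.4 and +4.5 to +4.7 points.

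**4. Error rate at the margin, blocked, without site:** 0.025, 0.022 to 0.023, 0.020 to 0.021 and 0.016 to 0.017. The planned test is conservative, never liberal. In a smaller simulation with unblocked schedules (7 sites, 6,000 trials per setting), it holds its level at 0.023 to 0.027, within simulation error.

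**5. Downside if site explains nothing, blocked.** With 12 unequal, unpooled sites, adding site loses up to about 0.7 point per co-primary and 1.4 for OSDI. In two such layouts, pooling sites under 8 subjects cut the loss to about 0.1 and 0.2.

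**6. Unblocked schedules, MGS**, at shares 0/5/10/20%:
- 8 sites of 16: 0.935 → 0.922, 0.938 → 0.935, 0.938 → 0.946, 0.941 → 0.965.
- 12 unequal sites, unpooled: 0.936 → 0.913, 0.936 → 0.925, 0.938 → 0.938, 0.941 → 0.960.

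Break-even lies at a share of roughly 5 to 10%, depending on layout.

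**7. Sensitivity to the meaning of SD.** If 8 and 14 are SDs before baseline adjustment and baseline explains an assumed 30% of variance, the residual SDs are 8 × √0.70 = 6.69 and 14 × √0.70 = 11.71. Planned power is then already higher, and the blocked gain at a 20% share falls to about +0.2 point per co-primary and +2.3 for OSDI.

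**The case against.** Baseline-only ANCOVA is a legitimate prespecified model, no stated figure is wrong, and Section 7.2.6 does look at site. On this view the point is only a preference. That stands as to severity: the sponsor may reasonably decline. It does not remove the point, because the poolability test puts no site term in the main models and a nearly free gain in precision need not correct an error.

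Four further objections narrow the point, and all of them stand:
- The gain needs two conditions, balance within site and residual site variance. Each site also measures baseline, so adjustment for it may already absorb part of any site difference.
- Section 7.2.4 does not say whether its SDs are before or after baseline adjustment. The reading used in steps 3 to 6 is the one more favourable to adding site.
- Short blocks carry a cost. The trial is open-label with sequential envelopes, so staff who know earlier assignments could guess later ones.
- Adding site alone to Section 7.2.7 would not align imputation with analysis, because treatment arm and baseline OSDI are also missing from its list.

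A reader might infer that omitting site inflates the false-positive rate or undermines the power statement. Steps 1 and 4 show neither. A reader might also set 80.1% OSDI power at a zero share beside 88.0% with site at a 20% share and see a gain of about 8 points. That is not like for like: at a 20% share the model without site already reaches about 83%.

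**Conclusion.** An optional improvement, not a defect. With blocked schedules and 7 to 8 sites, adding site is worth about 0 at a 0% residual site share, about +1 point per co-primary and +2.3 for OSDI at 10%, and about +1.7 and +4.6 at 20%.

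These figures rest on an assumed site share, blocks of 4, and the stated SDs being residual after baseline. The true gain could be nil or, with many small unpooled sites, slightly negative. The documents do not support treating the schedules as either blocked or unblocked, so the recommendation has to be conditional.

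**What to change.** 1. **Section 6.5:** state whether each site's schedule is blocked. If blocking is newly introduced, use varied block sizes and withhold them from sites.
2. **Sections 7, 7.2.1 and 7.2.2, if schedules are blocked:** fit arm + baseline + site, with site as a fixed factor. Fix a rule for pooling small sites before outcome data by arm are reviewed; for example, sites with fewer than 8 subjects form one group.
3. **Section 7.2.7, if site is added:** include every term of the analysis model in the imputation model, namely site (grouped the same way), treatment arm and the endpoint's own baseline, including baseline OSDI. Section 6.2 rules out imputation altogether, so the two sections need reconciling first.
4. **Section 7.2.6:** keep the site-by-treatment assessment as the poolability check.

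If the schedules are unblocked and cannot be changed, adding site is a trade-off and the baseline-only model can stand.

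**Cost:** text and code only, with no added subjects or visits. With blocking and 7 to 8 sites, or with small sites pooled, the power cost if site explains nothing is about 0.1 point per co-primary and 0.2 for OSDI. New blocking also brings some predictability of assignment, which varied block sizes reduce but do not remove.

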6.6 Treatment

The study procedure shall be performed on both eyes on the same day.

1. Eye makeup shall be removed.
2. The device shall be prepared for use in accordance with the Instructions for Use (IFU)/User Manual for the device to which the subject is randomized. An IFU/User Manual is packaged with each device that will be used in the study.

3. Anesthetic eye drops shall be instilled in both eyes.
4. Therapy shall be delivered in accordance with the IFU/User Manual for the device to which the subject is randomized.
5. For iLux device treatment, the following zones will be treated in the following order:
 - 5.1. upper lid, medial-nasal region
 - 5.2. lower lid, medial-nasal region
 - 5.3. lower lid, medial-temporal region
6. Representatives from the Sponsor may be present during the treatment but are not required.
7. Throughout the treatment visit, subjects will be assessed for any adverse events. Subjects will also be assessed for adverse events one hour following treatment, including for development of entropion or ectropion, floppy eyelids, and lash integrity assessment.
8. Following treatment, subjects will be assessed for the following:
 - Pain and discomfort using the questionnaires in Appendix C. These questionnaires must be self-assessed prior to any clinical evaluation.
 - Uncorrected Visual Acuity
 - BSCVA
 - Slit Lamp for Anterior Segment Health
 - Lid Margin Abnormalities
 - Eyelid Margin Assessment
 - Corneal Fluorescein Staining Slit Lamp Evaluation
 - Intraocular Pressure

6.7 1-Day Office Visit Follow-Up

Subjects will be required to be seen in person 1 day after the procedure for the following assessments:

- Discomfort and Pain Questionnaires (self-assessed prior to clinical evaluation)
- Uncorrected Visual Acuity
- BSCVA
- Slit Lamp for Anterior Segment Health
- Lid Margin Abnormalities
- Eyelid Margin Assessment
- Corneal Fluorescein Staining Slit Lamp Evaluation

Assessment for adverse events must include assessment for changes to eyelid margins (development of entropion or ectropion, floppy eyelids, and lash integrity assessment).

6.8 2-Week Office Visit Follow-Up

Subjects will be required to be seen in person 2 weeks (day 10-16) after the procedure for the following assessments:

- Discomfort and Pain Questionnaires (self-assessed prior to clinical evaluation)
- OSDI
- Uncorrected Visual Acuity
- Keratometry
- Manifest Refraction

- BSCVA
- Slit Lamp for Anterior Segment Health
- Lid Margin Abnormalities
- Eyelid Margin Assessment
- TBUT
- Corneal Fluorescein Staining Slit Lamp Evaluation
- Meibomian Gland Assessment and Scoring (must be performed by a masked rater)
- Intraocular Pressure

Assessment for adverse events must include assessment for changes to eyelid margins (development of entropion or ectropion floppy eyelids, and lash integrity assessment).

6.9 4-Week Follow-Up

Subjects will undergo the same screening assessments identified in Table 1 above at the 4-week visit. Specifically, the following tests will be performed:

- Discomfort and Pain Questionnaires (self-assessed prior to clinical evaluation)
- OSDI
- Uncorrected Visual Acuity
- Keratometry
- Manifest Refraction
- BSCVA
- Slit Lamp for Anterior Segment Health
- Lid Margin Abnormalities
- Eyelid Margin Assessment
- TBUT
- Corneal Fluorescein Staining Slit Lamp Evaluation
- Meibomian Gland Assessment and Scoring (must be performed by a masked rater)
- Intraocular Pressure

Assessment for adverse events must include assessment for changes to eyelid margins (development of entropion or ectropion floppy eyelids, and lash integrity assessment).

